Sample Size Justification The proposed sample sizes (6 patients for experiment #1, 15 patients for a within-group design in experiments #2-#4, or 25 patients for a between-groups design in experiments #2-#4) are primarily based on logistic considerations and conform to the exploratory (i.e., hypothesis-generating) nature of this pilot study. Because this is a pilot study, a formal sample size/power calculation is not required. Statistical Analyses For Experiment #1, descriptive analysis will be conducted to help inform the study design for the remaining experiments. The mean, standard deviation and morphology (either 3D reconstruction or number of MRI slices detecting a toxin effect) of BTME volume following injection in the LGM and MGM will be calculated for all 3 groups. If injections in the two muscles are similar (BTME volume +/- 20%) and there is no evidence of toxin movement outside of the injected muscle, then a within subject design will be implemented as described above. If not, we will use a between-subject design. Given the resources required for this study and the time commitment of the subjects, we propose a preliminary analysis for Experiments #2 and #3 after completion of MRI2 in 12 subjects if using a between subjects design (8 in each in standardized and 4 in the experimental injection groups using a 3:2 ratio) or 12 subjects if using the within-subjects design (12 comparison). For experiment #2 with a within-subjects design, we will examine the difference in BTME volume from baseline to 2 months following injection between the muscle sites injected with standard and experimental BT dilution in each patient using a paired t-test or Wilcoxon signed-rank test, as appropriate. For a between-subjects design, experiment #2 will be analyzed using a two-sample t-test or Wilcoxon rank sum test, as appropriate, to compare the mean 2-month difference in BTME volume in patients who received a standard dilution injection vs. those who received an experimental dilutio8n/15i/n1j9e4c:t0io6nPM in the spastic LGM. For either a within- or between-subjects design in experiment #3, we will use the paired t-test or Wilcoxon signed-rank test, as appropriate, to examine the difference in BTME volume from baseline to 2 months following injection between the spastic and non-spastic muscle sites injected in each patient. Experiment #4 will be analyzed descriptively, showing mean, standard deviation, median, and range of 2-month change in BTME volume for each combination of clinically injected site, dose, and dilution. This information will be used to generate hypotheses for future studies. Observational Group: N=6 observational subject MRI data will be analyzed the same as data from Experiment #4. All p-values will be two-sided with statistical significance evaluated at the 0.05 alpha level. Ninety-five percent confidence intervals for means will be calculated to assess the precision of the obtained estimates. Lack of any observed statistically significant differences between groups will not constitute evidence of equivalence or non-inferiority between dilution or spasticity groups; rather, estimates in each group will serve as preliminary data for further investigation (i.e., hypothesis-generating). All analyses will be performed in SAS Version 9.4 (SAS Institute, Inc., Cary, NC). Note: The statistical analysis section was written in conjunction with [name], MS, in the Division of Biostatistics and Epidemiology, Department of Healthcare Policy & Research.

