
The research questions for the present study series are as followed:

1. How does the movement and morphology of BT muscle effect (BTME) differ between standardized, research injections into spastic and non-spastic LGM?

2. How does the movement and morphology of BTME differ between a standardized, research injection into spastic LGM versus an injection using the same dose in a 100% greater dilution?

3. Is there a predictable BTME within a given muscle following lower extremity BT clinical injections based on clinical need?

We have two hypotheses.

First, we predict that BT muscle effect (BTME) will be greater in normal muscle than in spastic muscle.

Second, we hypothesize that BTME will increase with increasing dilution.

The standard BT injection will be an injection of 25 units of onobotulinumtoxinA (Botox[®]) diluted in 0.25cc of saline.

The experimental BT injection will be an injection of 25 units of onobutilinumtoxinA (Botox[®]) diluted in 0.50cc of saline.

Four experiments will be conducted to explore the research questions. At baseline, subjects will receive research injections that are decided based on the research protocol. Given the very small dosage of the research BT injections, we do not anticipate seeing any symptomatic effects in subjects. At 3 months following research injections, subjects will receive clinical injections that are decided based on their clinical need and are anticipated to result in clinical benefit for subjects. For all experiments subjects will have an MRI at baseline (MRIB), at 2M following research injections (MRI2), and at 2M following clinical injections (MRI3). If, for enrolled subjects who have previously had botulinum toxin injections below the knee, evidence of present botulinum toxin effect is seen on MRI, the subject will be ineligible for the research injections, MRI2, and MRI3 and will instead be offered to receive the clinical injections and then be exited from the study.

Experiment #1:

After a baseline MRI, 6 subjects will be randomized into three groups (N=2 in each group): standard injection in LGM, experimental injection in LGM, or experimental injection in MGM. All 6 subjects will receive a standard injection to the non-spastic LGM. Subjects will undergo a second MRI 2 months after the research injections, which will be used to confirm the design of the subsequent experiments.

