If, for Experiment #1, we find on MRI2 a similar appearance and volume of BTME (BTME volume +/-20%) for both the LGM and MGM receiving the experimental injection and that the BTME is contained within each muscle, we will have the option of proceeding with the within- subject design where each subject serves as his or her own control, receiving either the research or experimental injection in the spastic LGM and the alternative injection in the spastic MGM. If the within-subject design is used, 15 subjects will be recruited. If the BTME volumes for the LGM and MGM receiving the experimental injection are not within +/- 20% of each other, or we see on the MRI that the BTME is not contained within each injected muscle, then we will use a between subject design where subjects will be randomized to receive either the experimental or standard injection to the spastic LGM and 25 subjects will be recruited.

Subjects will receive clinical injections 3 months following the research injections and undergo a final MRI 2 months following clinical injections. Recruitment for the subsequent experiments will begin after data analysis from the second MRI in experiment #1 is complete.

Experiment #2 (Effect of dilution, answer Research Question #1):

If using a within-subject design, subjects will be randomized to receive a standard injection to either the LGM or MGM. The experimental injection will be delivered to the muscle not receiving the standard injection. If using a between-subjects design, subjects will be randomized to receive either a standardized injection in the LGM or an experimental injection in the LGM. On the same day of, but before the injection, the MRIB will be acquired. Using the localization schema proposed in our proof-of-concept study, the baseline scan will be used to determine the coordinates and depth of the injection into a given muscle. Two months (+/- 1 week) after the injection, subject will report for MRI2 and will be considered finished with Experiment #2.

He/she will be scheduled for the "clinical" injection 5 weeks (+/- 1 week) from that time, which will be evaluated in Experiment #4.

Experiment #3 (spastic vs. non spastic muscle, answer Research Question #2):

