Experiment #3 will take place simultaneously and within the same subject population as Experiment #2. Regardless of whether a within- or between subject design is adopted in Experiment #2, all subjects will also receive a standard injection to the non-spastic LGM. The same technique using MRIB for muscle localization and the same protocol for obtaining MRI2 employed in Experiment #2 will be used for Experiment #3, at the same time points. Subjects will be scheduled for the "clinical" injection 5 weeks (+/- 1 week) from the time of MRI2, as mentioned under the description for Experiment #2.

Experiment #4:

As described previously, all subjects that participated in Experiments #2 and #3 will undergo a cycle of clinically-based BT injections to the spastic lower extremity no sooner than 3 months after the research injections and about 1 month after MRI2. Potentially, any lower extremity muscle or combination of muscles may be injected based on clinical evaluation and need. We reserve the right to limit the total dose of toxin injected to no more than 200 units of onobotulinumtoxinA. This would be a reasonable dose in clinical practice for the first cycle of lower extremity injections in a toxin-naive patient. All subjects will receive a third and final leg MRI3 2 months following the clinical injection, marking the end of this study approximately 5 months after the initial randomization in Experiment #2.

Observational Descriptive Study

An additional N=6 subjects who are receiving onobotulinumtoxinA injections in their lower leg on their spastic side for clinical purposes as part of standard clinical care will be recruited from the PI's clinical population. Qualifying subjects will be patients who are receiving onobotulinumtoxinA injections for any lower extremity muscle or combination of muscles and are naïve to previous onobotulinumtoxinA injections in the lower extremity. Subjects participating in this observational portion of the study will be

asked to undergo to MRI exams of their legs, one prior to their clinical onobotulinumtoxinA injections and one two months post injection. The research team will document the muscle groups injected and the dosage and dilution of the injections for data analysis purposes.

The reasoning behind adding this additional group of subjects is threefold:

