1. We plan to use these additional data to practice and refine our interpretation of MRI images in preparation for analysis of the MRI images of subjects participating in Experiments 1-4

2. We plan to use these additional data to inform Research Question 3 (Is there a predictable BTME within a given muscle following lower extremity BT clinical injections then expected based on clinical need?)

3. We have had greater difficulty prospectively recruiting subjects for Experiments 1-4 and believe we will be more successful in recruiting subjects and obtaining data for this observational subject group while we continue to recruit for Experiments 1-4.

INCLUSION AND EXCLUSION CRITERIA

Experimental Group: Subjects will include males and females aged 30-75 with the diagnosis of any stroke (ischemic or hemorrhagic, first occurrence or recurrent) with clinically significant lower extremity spasticity as assessed by the principal investigator who would benefit from treatment with BT. Subjects must be ambulatory with or without a device and without assistance at a household or greater level. Any combination of spastic lower extremity muscle injections are acceptable so long as there is an indication to inject the gastrocnemius muscle. The goals of treatment may include improvement of gait, ankle range of motion, ankle foot orthosis fit, heel strike, and ankle position in stance phase. Also, decreased clonus or relief from painful muscle spasms may be goals. Subjects will be naïve to BT of any serotype, as well as, phenol or alcohol treatment in any lower extremity muscle for any reason. Prior upper extremity treatment is allowed, however.

Observational Descriptive Group: Subjects will include males and females aged 30-75 receiving clinical injections for any lower extremity muscle or muscle group with the diagnosis of spasticity of any etiology. Subjects must be ambulatory with or without a device and without assistance level at a household or greater. Subjects must be naive to botulinum toxin in the lower extremity only.

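### Experiment #4 does not separate research-injected gastrocnemius heads from other muscles, or name the scan from which its 2-month change in BTME is taken

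*Combined protocol and SAP*

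**What the plan says.** All places are in the Combined protocol and SAP.

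- **Population.** Experiment #4 takes its subjects from the earlier experiments: "all subjects that participated in Experiments #2 and #3 will undergo a cycle of clinically-based BT injections to the spastic lower extremity".
- **Earlier injection.** Under Study Design, "The standard BT injection will be an injection of 25 units of onobotulinumtoxinA (Botox[®]) diluted in 0.25cc of saline"; the experimental injection has the same dose in 0.50 cc. In the between-subjects design, "subjects will be randomized to receive either the experimental or standard injection to the spastic LGM and 25 subjects will be recruited". In the within-subject design each subject has both heads injected, "receiving either the research or experimental injection in the spastic LGM and the alternative injection in the spastic MGM". All subjects also receive a standard injection in the non-spastic LGM (Experiment #3).
- **Clinical target.** Under Inclusion and Exclusion Criteria, any combination of spastic leg muscles is acceptable "so long as there is an indication to inject the gastrocnemius muscle".
- **Scans.** MRIB is taken on the day of the research injection, MRI2 two months later, and MRI3 two months after the clinical injection. No scan is scheduled just before the clinical injection.
- **Analysis.** The Statistical Analyses section describes Experiment #4 by the mean, SD, median and range of the 2-month change in BTME volume for each clinical site, dose and dilution. The research injection and the reference scan are not mentioned. For the observational group, "N=6 observational subject MRI data will be analyzed the same as data from Experiment #4".
- **Earlier toxin at entry.** For enrolled subjects injected below the knee before the study, if "evidence of present botulinum toxin effect is seen on MRI, the subject will be ineligible for the research injections". No matching check precedes the clinical cycle.

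**The concern.** The entry criterion makes the gastrocnemius an expected clinical target, and that muscle carries the research injection. BTME, as defined for the proof-of-concept study (the only definition given), counts every voxel at least 3 SD above the baseline mean, so it cannot show which of two injections made a voxel abnormal. At entry the protocol treats visible earlier toxin effect as a reason not to proceed with the research measurements, but the Experiment #4 analysis is silent on the same issue.

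Research Question 3 is at stake: whether BTME within a muscle is predictable after clinical injections. In a head injected in both cycles, the tabulated figure could depend on the research injection and its randomized dilution as well as on the clinical site, dose and dilution that label the row. Observational subjects are toxin-naive in the leg and are scanned before and two months after their only injection, so the same clinical injection could give different figures in the two groups because of research history alone.

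**Working it through.** **1. Timeline, reproducing the plan's figure.** Inputs: MRI2 at 2 months ± 1 week and clinical injection 5 ± 1 weeks later (Experiment #2); MRI3 2 months after that (Experiment #4). One month = 365.25 / 12 / 7 = 4.35 weeks, so 2 months = 8.7 weeks. The plan gives no window for MRI3 and none is added.

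| Weeks from research injection | Earliest | Nominal | Latest |
|---|---|---|---|
| MRI2 | 7.7 | 8.7 | 9.7 |
| Clinical injection | 11.7 | 13.7 | 15.7 |
| MRI3 | 20.4 | 22.4 | 24.4 |

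Nominal MRI3: 8.7 + 5 + 8.7 = 22.4 weeks, or 5.15 months (range 4.69 to 5.61). This agrees with the plan's approximate 5 months.

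**2. Against the stated duration.** The risk text in the Data and Safety Monitoring Plan puts toxin effects at about 12 weeks. The clinical injection falls 13.7 − 12 = 1.7 weeks after that (range −0.3 to 3.7) and MRI3 falls 22.4 − 12 = 10.4 weeks after it (range 8.4 to 12.4). Separately, the windows allow a clinical injection at 11.7 weeks, while Experiment #4 says no sooner than 3 months (13.0 weeks). These passages must be reconciled.

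**3. What the 2-month change could mean.** MRI2 precedes MRI3 by 5 + 8.7 = 13.7 weeks and MRIB precedes it by 22.4 weeks. Neither is 2 months before MRI3, so the wording does not identify the reference scan.

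**4. Error under each reference scan.** For a head injected in both cycles, let C be the BTME volume due to the clinical injection, V the research BTME at MRI2, r the fraction of V still above threshold at MRI3, and o the part of that residue that the clinical injection also affects (counted once). BTME at MRIB is taken as zero.

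- MRI3 BTME = C + rV − o
- Measured from MRIB, the error is rV − o, between 0 and rV. So rV is an upper bound, reached only with no overlap.
- Measured from MRI2, the error is rV − o − V = −(1 − r)V − o, an understatement.

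Illustration with V = 100 and o = 0 (assumed; r is not in the documents):

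| r | C = 100, from MRIB | C = 100, from MRI2 | C = 200, from MRIB | C = 200, from MRI2 |
|---|---|---|---|---|
| 0 | 100 | 0 | 200 | 100 |
| 0.10 | 110 | 10 | 210 | 110 |
| 0.25 | 125 | 25 | 225 | 125 |
| 0.50 | 150 | 50 | 250 | 150 |

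With no residue at all, MRIB gives the right answer and MRI2 is wrong by the whole of V. The choice of reference scan therefore matters even if there is no carry-over.

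**5. Scale from MRIB.** The plan says of the clinical cycle: "We reserve the right to limit the total dose of toxin injected to no more than 200 units of onobotulinumtoxinA". One research site is 25 / 200 = 12.5% of that total and two are 50 / 200 = 25%. The gastrocnemius share of the clinical dose is not given. If BTME were proportional to dose (assumed), the largest overstatement for one site is r × 25 / (clinical dose in that head). Over 25 to 200 units:

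- r = 0: 0%
- r = 0.10: 10% down to 1.25%
- r = 0.25: 25% down to 3.1%
- r = 0.50: 50% down to 6.25%

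**The case against.** The strongest reply is that the design already leaves time for the research effect to go. The clinical injection is planned for no sooner than 3 months, MRI3 comes 2 months after that, and on the 12-week figure the research effect has ended some 8 to 12 weeks before MRI3. This largely stands as a reason to expect little residue. It is not complete. The 12 weeks is a general figure in the risk text. The protocol expects no symptomatic effect from the research injections yet schedules MRI2 to image their BTME, so symptom duration cannot stand in for T2 duration. It also does not answer the MRI2 problem, which is largest when the residue has gone.

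Several stronger readings are tempting, and the documents do not support them:

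- *That Experiment #4 will overstate clinical BTME.* The direction depends on a reference scan that is not named.
- *That residue has been shown.* The proof-of-concept study scanned at 3 months, but the text gives a scan date and no finding of persistence then or later.
- *That all 15 or 25 subjects' results are affected.* Only research-injected heads that are also injected clinically are at issue, plus any neighbouring muscle reached by spread. Entry requires an indication for the gastrocnemius, not for a particular head.
- *That observational data will be pooled with Experiment #4.* Analysing them the same way does not say so.

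Finally, no hypothesis test or study decision rests on Experiment #4. That stands and limits the severity.

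**Conclusion.** The point holds as an omission with an unknown and possibly small effect. The analysis of Experiment #4 does not distinguish gastrocnemius heads that had a 25-unit research injection about 5 months before MRI3, and it leaves open a reference scan that decides the direction of any error. From MRIB the error lies between zero and the residual fraction of the MRI2 BTME. From MRI2 it is an understatement of at least the faded part of that BTME. The residual range of 0 to 0.5, proportionality to dose and zero BTME at MRIB are assumptions of this review, and nothing in the documents supports the upper end of that range. Severity is low: the output is descriptive and hypothesis-generating. It does feed Research Question 3, and the remedy is cheap.

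**What to change.** Add to the Experiment #4 paragraph of Statistical Analyses:

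- (a) BTME change at MRI3 is measured from MRIB.
- (b) Research-injected gastrocnemius heads are summarised separately from muscles with no research injection. Observational gastrocnemius data are combined or compared with the research-injected heads only if no residual is seen.
- (c) Where MRI3 images both legs, BTME in the non-spastic LGM at MRI3 and its ratio to MRI2 are reported as an approximate check on carry-over. That muscle has the standard research injection, and the clinical injections go to the spastic limb. State the limits: it covers non-spastic muscle, where the protocol predicts greater BTME, and the standard dilution only.
- (d) As a sensitivity analysis, MRI3 BTME in research-injected heads is reported with and without voxels already above threshold at MRI2. Removing them understates clinical BTME where the two effects truly overlap, so both figures are shown.

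The cost is wording and further reading of planned scans. For (c) the sponsor must confirm that MRI3 covers both legs, since the protocol speaks only of a leg MRI. There will be fewer observations per summary row. Under the within-subject design every spastic LGM and MGM has had a research injection, so Experiment #4 has no unexposed gastrocnemius stratum and (c) and (d) carry the check there.

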
5 subjects, the muscles of interest were manually outlined on T2 maps at baseline, whereas 2M and 3M post-injections were mapped using software written in-house in IDL 8.1 (Exelis Inc, Boulder, CO). A histrogram of T2 relaxation times (ms) was constructed for the baseline scan for all voxels in the muscle. A Guassian function was used to calculate a mean and standard deviation for each muscle at baseline. We defined BTME a priori as only those voxels on subsequent scans with a T2 relaxation time ≥ 3 standard deviations (SD) above the baseline mean for that subject and muscle. Subject specific thresholds were required due to variation among both subjects and muscles. Knowing 8th/1e5/n19um4:0b6ePr M of abnormal voxels in a given muscle after BT inject for each MRI slice, a per muscle/per slice BTME volume (at .0015 voxel) could be calculated for each muscle and subject.

STUDY DESIGN

The primary objective of this series of experiments is to, in a research setting, better understand how spastic muscle and differing dilutions affect BT movement through muscle.

The secondary objective of this series of experiments is to, in a clinical setting, describe BT movement through a variety of lower extremity muscles with differing doses and dilutions of BT commonly used in clinical practice.

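### The six observational patients' scans both refine the MRI reading and serve as descriptive evidence for Research Question 3, with no masked reading and no reading rule fixed for this study

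*Combined protocol and SAP*

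**What the plan says.** The Observational Descriptive Study section adds six patients who receive clinical injections in routine care and have one scan before and one two months after injection. The team records the muscles injected, the dose and the dilution. The section gives three reasons for adding them:

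- Practice: "We plan to use these additional data to practice and refine our interpretation of MRI images", as groundwork for reading the scans of Experiments 1-4.
- Evidence: "We plan to use these additional data to inform Research Question 3", which asks whether BTME (the botulinum toxin muscle effect on MRI) is predictable after clinical injection.
- Feasibility: the team expects more success in recruiting and in "obtaining data for this observational subject group while we continue to recruit for Experiments 1-4".

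The Statistical Analyses section adds that "N=6 observational subject MRI data will be analyzed the same as data from Experiment #4". For that experiment, "Experiment #4 will be analyzed descriptively, showing mean, standard deviation, median, and range of 2-month change in BTME volume". The summaries are broken down by site, dose and dilution.

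The reading method is described only in the background account of the proof-of-concept series. There, "the muscles of interest were manually outlined on T2 maps at baseline", later scans were mapped with in-house software, and the threshold was set in advance, relative to a mean specific to each patient and muscle: "We defined BTME a priori as only those voxels on subsequent scans with a T2 relaxation time ≥ 3 standard deviations (SD) above the baseline". The Statistical Analyses section does not restate any of this for the present study. It leaves morphology open between a 3D reconstruction and a count of slices.

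**The concern.** Every result in this study is a reading of an MRI scan. If a reading method is adjusted on a set of scans whose injection records are known, summaries from that same set are partly a product of the adjustment. Presenting them as evidence on whether BTME is predictable treats development data as a result.

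Two further gaps make this more than a labelling matter. Nothing says that refinement must be finished before scans from Experiments 1-4 are read, so values read at different times might not be the same measure. And nothing hides dilution or injection record from the reader, although the Study Design section states directional hypotheses for both tested comparisons: more effect in normal than in spastic muscle, and more effect with greater dilution.

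At stake are the descriptive summaries that are meant to generate hypotheses, the Experiment #1 reading that selects the design and the sample size (15 or 25), and the Experiment #2 and #3 comparisons at two-sided 0.05.

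**Working it through.** The plan gives no figure to reproduce here, and it states that no formal power calculation was made. The check is mainly a comparison of texts, with two small calculations.

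**1. Dual use.** The practice reason and the evidence reason name the same six patients. Nothing sets some aside for practice and others for evidence. The dual use is explicit.

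**2. Timing.** The practice reason puts refinement ahead of the analysis of Experiments 1-4. The feasibility reason has recruitment running in parallel. Two steps inside Experiments 1-4 depend on readings made along the way:

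- the Experiment #1 decision (BTME volumes within +/-20% and effect contained within the muscle), which must be analysed before recruitment to the later experiments begins;
- the preliminary analysis of Experiments #2 and #3 after the second MRI in 12 subjects.

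No sentence says that refinement ends before either step, or that scans already read are read again.

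**3. What is fixed and what is left to judgement.** If the proof-of-concept rule were carried over, the voxel threshold would be fixed. The following would stay open: how similar appearance and containment are judged, which morphology measure is used, and what counts as residual toxin effect at enrolment in a previously injected patient. A threshold relative to a pre-injection scan does not answer that last question.

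**4. Masking.** No section describes reading without knowledge of dilution, injected muscle or clinical injection record.

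**5. Extent of overlap.** With n patients contributing clinical-injection scans from the experiments, the six make up 6/(6 + n):

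| Patients counted | n | Share |
|---|---|---|
| Within-subject design | 15 | 6/21 = 28.6% |
| Between-subject design | 25 | 6/31 = 19.4% |
| Within-subject, plus 6 from Experiment #1 (assumption) | 21 | 6/27 = 22.2% |
| Between-subject, plus 6 from Experiment #1 (assumption) | 31 | 6/37 = 16.2% |

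These shares measure overlap, not bias. They also assume a pooled count that the plan does not state.

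**6. Illustration of sensitivity to the rule.** Assume baseline voxel values follow the Gaussian used in the proof-of-concept series. The share of unaffected voxels above a cut-off of k SD is 1 − Φ(k):

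- k = 3: 0.135%
- k = 2.5: 0.62%, or 4.6 times as many

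The documents propose no cut-off other than 3 SD. How much such a change would move BTME volume depends on the size of the muscle, which is not given. This shows only why the rule should be stated and kept. It does not estimate an error in this study.

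**The case against.** The strongest reply has four parts.

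- **Refinement is described as preparation.** The stated order is practice first, analysis second. Parallel recruitment is not parallel reading. This stands: a change of rule during the study is something the text allows, not something it plans. A reader might infer that the rule will move after Experiment #2 or #3 scans have been read, but no sentence says so.
- **Nothing is tested on these six.** A reader might infer that a reading rule is being validated on its own training data. The documents do not support that. Experiment #4 and the observational group are summarised descriptively, with no hypothesis test and no claim to validate a rule, and the Experiment #2 and #3 tests do not use these patients. This stands. What remains is that a descriptive summary can still be shaped by tuning, and that the tested comparisons rely on the refined reading even though they do not use the practice scans.
- **The proof-of-concept method has safeguards.** Outlining was done on baseline scans, later scans were mapped by software, and the threshold was set in advance. Carried over, these would limit drift considerably. But they are reported only as what was done in that series, and the judgements in item 3 of the working lie outside them.
- **The overlap shares presuppose pooling.** The observational group has its own label in the Statistical Analyses section and is analysed like Experiment #4, not stated to be combined with it. This stands, so the shares are not planned quantities.

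It is also tempting to say that tuning will make BTME look more predictable than it is. The team knows where toxin was injected. Where it moves is what the study sets out to learn, so the direction of any bias cannot be asserted.

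**Conclusion.** The point holds in a limited form. The six patients' scans serve both to refine the reading and as descriptive evidence for Research Question 3, so those summaries partly reflect the data used for tuning. A mid-study change in reading is possible because nothing excludes it. The safeguards that would limit it are not adopted for this study, and reading is not masked although the team holds directional hypotheses.

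The overlap is six patients. As a share it would be between 16.2% and 28.6%, depending on the design and on whether Experiment #1 patients count, and only if the groups were combined. Neither the direction nor the size of any bias can be determined from the documents.

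In an exploratory pilot this does not undermine the study. It is a cheap improvement worth making, because it protects the one kind of measurement on which every result depends. The conclusion rests on the documents containing no reading manual. If a dated one exists elsewhere and masks the reader, citing it would answer much of the point, but not the dual use.

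**What to change.** 1. **Coded reading (Statistical Analyses).** Have outlining, BTME volume and containment scored on coded scans that hide dilution, which muscle was injected and the clinical injection record. Unmask only after the BTME values are locked. Anatomy stays visible, so the code hides what a muscle received, not which muscle it is.
2. **Separate status for the six (Statistical Analyses and Observational Descriptive Study).** Report them separately as development data, and do not count them as evidence of predictability for Research Question 3. Their eligibility is also wider (any cause of spasticity, not only stroke), which is a second reason to keep them apart.
3. **A stated rule (Statistical Analyses).** Adopt the proof-of-concept rule, with the 3 SD threshold and baseline outlining, for this study. If refinement changes it after any scan from Experiments 1-4 has been read, re-read those scans under the final rule. Report the Experiment #1 re-read as a consistency check that does not reopen the design choice already made.

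The cost is file coding, some re-reading, and possibly a short delay to the preliminary analysis. The evidence base for Research Question 3 is smaller by six patients. No additional patients or scans are needed, and the six patients' data are still reported.
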